4.7.3 Early Termination Visit

If a participant withdraws from the clinical trial, an Early Termination Visit will be arranged if possible with study staff. This will include:

- Assessment of new and ongoing AEs;
- Assessment of any complications following the study intervention;
- Performance of other relevant study-related procedures.

The PI and/or QI will ensure the participant is appropriately transitioned/followed for any additional care as required.

4.7.4 Participants who are Lost to Follow -up

A participant will be considered lost to follow-up if they fail to return for 2 scheduled visits and is unable to be contacted by the research team.

The following actions will be taken if a participant fails to attend a required study visit:

- The research team will attempt to contact the participant and reschedule the missed visit within 2 weeks, counsel the participant on the importance of maintaining the assigned visit schedule, and reconfirm whether the participant wishes to and/or should continue in the clinical trial.
- Before a participant is deemed lost to follow-up, the research team will make every
 effort to regain contact with the participant (where possible, three telephone calls
 and, if necessary, a certified letter to the participant's last known mailing address or
 local equivalent methods). These contact attempts should be documented in the
 participant's research record and/or legal health record.
- Should the participant continue to be unreachable, they will be considered to have withdrawn from the clinical trial with a primary reason of lost to follow-up.

MLHC study

5.0 **STUDY INTERVENTION**

5.1 Description

MLHC is delivered virtually through one-on-one meetings with the CRE offered over multiple sessions. The full program consists of 6 sessions across 12 weeks, covering all topics (geared towards new COPD diagnosis). The topics covered in the program include: general COPD knowledge, smoking cessation, COPD medications (inhalers, oxygen), physical activity, mental health and wellness, vaccinations, symptom selfmanagement skills (breathing, energy management, symptom monitoring), nutrition, travel, and long-term planning (including end-of-life care). As participants complete their virtual MLHC program with CREs, they will also have access to the Epic Care Companion app developed as a companion app to MLHC. This app will display a section for each MLHC program session completed, along with session-specific educational and self-management tasks for the patient to complete after the session. These will mostly consist of links to session-specific educational content, but there will also be medication reminder notifications, and reminders to discuss specific topics with their respiratory healthcare providers. This app may also contain individualized tasks created between the CRE and MLHC participant during their sessions. A final report of all completed tasks will be generated on program completion and available in the participant's Epic electronic health record, which can be reviewed by their respiratory healthcare providers.

5.2 Treatment Regimen

MLHC will be delivered virtually through secure videoconferencing software (Zoom) by CREs. Participants will be contact by the CREs to organize an acceptable program schedule. Ideally, participants will have 1 session every 2 weeks, for a total of 6 sessions over 12 weeks. They will be free to engage with the MLHC Care Companion app at their own leisure throughout this period and after program completion.

5.3 Method for Assigning Participants to Treatment Groups N/A – single arm study

5.4 Administration of Study Intervention

MLHC will be delivered virtually through secure videoconferencing software (Zoom) by CREs as detailed above. All onboarding for the virtual program will be completed by the CREs. Upon study consent, patients will also be oriented to the use of the MLHC Care Companion app by study staff virtually or in-person. They will be shown how to download and login to the Epic Care Companion app, and how to navigate through the MLHC materials. Any tech support needed throughout the study will also be provided by study staff at WCH.

5.5 Participant Compliance Monitoring

Participation in the virtual MLHC program will be tracked by the CREs using standardized forms (using the Lung Health Foundation's Salesforce architecture developed for MLHC administration). This information will be securely sent to WCH and

MLHC study

integrated into Epic in collaboration with the Womens' Virtual Care Research Laboratory. Use of the Epic Care Companion MLHC companion app will be tracked internally at WCH.

5.6 Concomitant Therapy

COPD medication use/treatments (inhalers, antibiotics, prednisone, and oxygen) will be recorded at baseline, at 3 months follow-up, and at 6 months follow-up.

5.7 N/A	Packaging
5.8 N/A	Blinding of Study Intervention
5.9	Receiving, Storage, Dispensing and Return
5.9.1 N/A	Receipt of Study Intervention Supplies
5.9.2 N/A	Storage
5.9.3 N/A	Dispensing of Study Intervention
5.9.4 N/A	Return or Destruction of Study Intervention

6.0 RESEARCH PROCEDURES

6.1 Research Visits

- Pre-Screening Visit / Screening Visit (virtual or in-person)
 - Informed consent
 - Review of eligibility criteria
 - Orientation to the Epic Care Companion MLHC companion app
 - This visit will be performed by study staff (research assistant, or study investigators)
- Baseline Visit (virtual)
 - Collection of baseline outcome data
 - This visit will be performed by CREs as part of the MLHC program, study staff (research assistant, or study investigators) will confirm data collection and if needed supplement data collection using Epic or by contacting the participant

MLHC study

- Delivery of MLHC program 6 virtual sessions over 12 weeks, delivered by CREs, no outcome collection during this phase of the study
- Follow-up Visit at 3 months post baseline (virtual)
 - o Collection of follow-up outcome data
 - This visit will be performed by CREs as part of the MLHC program, study staff (research assistant, or study investigators) will confirm data collection and if needed supplement data collection using Epic or by contacting the participant
- Follow-Up Visit at 6 months post baseline (virtual)
 - o Collection of follow-up outcome data
 - This visit will be performed by CREs as part of the MLHC program, study staff (research assistant, or study investigators) will confirm data collection and if needed supplement data collection using Epic or by contacting the participant

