6.2 Schedule of Events

Procedures	Screening Day -7 to -1	Baseline Visit 1, Day 1	Study Visit 2, 3 months	Study Visit 3, 6 months
Informed consent	X			
Confirming eligibility	X			
MLHC companion app orientation	X			
Demographic information	X			
Health system utilization		Χ	X	X
COPD severity (CAT and mMRC scores)		X	Х	X
Health-related quality of life (CAT score)		X	X	X
Mediation review		X	X	X
Smoking status review		Χ	X	X
Vaccination status review		Χ	X	X
Adapted COPD-Q score (knowledge of COPD)		Χ	X	X
Adapted COPD Self-Efficacy score		Χ	X	X
Partners in Health Scale score (self-management)		Χ	Χ	X
COPD referrals review (rehab, smoking cessation)		X	X	X
Adverse event review and evaluation		X	Х	X
Complete Case Report Forms (CRFs)	X	X	X	X

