7.4.3 Analysis of the Secondary Endpoint(s)

Clinical endpoints:

Assessed prior to study start, at 3 months (end of MLHC program) and at 6 months (follow-up after program completion). Outcomes will be collected by MLHC CREs using a standardized form in Salesforce, as well as a research assistant based on Epic electronic chart review. For continuous variables, difference in the mean (SD) will be calculated at 3 months and 6 months compared to baseline. For dichotomous variables, difference in proportions at 3 and 6 months compared to baseline will be calculated.

MLHC study

- Healthcare system utilization (number of COPD-related outpatient visits, hospital admissions, ED visits, ICU admissions (at baseline will be over the previous 12 months)
- COPD severity (CAT and mMRC scores, and number of COPD exacerbations)
- Health related quality of life (CAT score)
- COPD medication use (COPD controller medication use, oxygen therapy, oral corticosteroid use, antibiotic use, rescue inhaler use)
- Smoking status (packs per year, quit attempts)
- Vaccination status (routine guidelines recommended vaccines received)
- COPD knowledge (Adapted COPD-Q score)
- Self-efficacy score (Adapted COPD Self-efficacy scale score)
- Self-management score (Partners in Health Scale score)
- Healthcare provider referrals prior to using the program (pulmonary rehab, smoking cessation counseling referrals

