10.0 DATA HANDLING AND RECORD KEEPING

10.1 Source Documents & Case Report Forms

Please reference this study's Data Management Plan (DMP).

Data for this clinical trial will be managed using REDCap electronic case report forms. This system is maintained on central WCH servers with data backed up daily, and is supported by the WCH REDCap Administrator.

This study will involve the collection of system use and clinical data by study staff (which may include PI, co-investigators, or research assistants) from securely transferred data collection from CREs, medical records from EPIC, and/or REDCap questionnaires in order to evaluate system feasibility and effectiveness. CRE notes from participation in the MLHC program will be kept in LHF servers and transferred securely to WCH servers.

The personal health information (PHI) required for this study is described in the Patient Data collection form. PHI is required for this study because we are evaluating measures of clinical effectiveness in order to inform future larger trials.

MLHC study

10.2 **Protocol Deviations**

No deviations from or changes to the protocol will be implemented without prior agreement from the sponsor as required, and approval from the REB, unless to eliminate an immediate hazard to a participant.

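### The educators who coach participants also run the 3- and 6-month outcome visits, so the self-reported change scores are liable to reporting bias, probably favourable and of unknown size

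*Protocol*

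**What the plan says.** Protocol section 6.1 describes the programme as "6 virtual sessions over 12 weeks, delivered by CREs, no outcome collection during this phase of the study". In the same section the baseline, 3-month and 6-month visits each carry the same statement: "This visit will be performed by CREs as part of the MLHC program". Study staff have a secondary role at these visits: they "will confirm data collection and if needed supplement data collection using Epic or by contacting the participant".

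Sections 3.3 and 7.4.3 agree on who collects the clinical outcomes: "Outcomes will be collected by MLHC CREs using a standardized form in Salesforce, as well as a research assistant based on Epic electronic chart review". The schedule in section 6.2 places the CAT, mMRC, adapted COPD-Q, adapted COPD Self-Efficacy and Partners in Health scores at all three visits.

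The effect measure in section 7.4.3 is the difference from baseline at 3 and 6 months. Section 3.1 states that there is no control group. Section 10.1 lists the data sources as secure transfers from the CREs, "medical records from EPIC, and/or REDCap questionnaires", without saying which instruments would come by REDCap or who would complete them.

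**The concern.** These five scores rest on what the participant reports. At baseline the participant answers a CRE before any coaching. At 3 and 6 months, after six one-on-one sessions, the participant answers a member of the group that taught the material and encouraged the behaviours being scored. A wish to please, or to give the taught answer, can therefore act at follow-up and not at baseline.

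Three uses of the scores are exposed:

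- The secondary objective (section 2.2) is to look for clinical benefit by comparing values before and after the programme.
- Section 7.2 says the results will inform the sample size of a later controlled trial. If the raw mean change were taken as the target effect, an optimistic value would make that trial too small, because sample size varies with the inverse square of the target difference.
- Section 7.4.4 looks at COPD severity scores for safety signals. If symptoms were understated to the coaching staff, a deterioration could be harder to see.

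Who collects an outcome is settled by the protocol, and a later analysis cannot undo it.

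**Working it through.** **1. Roles side by side**

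| Task | Who | Protocol section |
|---|---|---|
| Six coaching sessions | CREs | 5.1, 5.2, 6.1 |
| Outcome visits at baseline, 3 and 6 months | CREs | 6.1 |
| Entry of outcomes on the Salesforce form | CREs | 3.3, 7.4.3 |
| Chart review | Research assistant | 3.3, 7.4.3 |
| Confirming and supplementing data | Study staff | 6.1 |

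Chart review can corroborate admissions, visits and prescriptions. It is no evident independent source for knowledge, self-efficacy or self-management scores. Confirming that data were collected does not show how the answers were obtained. No passage separates coaching from the administration of these questionnaires.

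**2. Why CRE collection at baseline does not cancel the bias**

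Let D be the true mean change, b0 the reporting bias at baseline and b1 the bias at follow-up. The expected observed change is D + (b1 − b0). Using the same staff group throughout removes only the part of the bias common to both occasions. The part that arises from having been coached exists only at follow-up and stays in the change. With one arm, nothing in the design estimates it.

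**3. Illustration of sensitivity**

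The plan has no figure to reproduce: section 7.2 chooses 50 participants without a calculation, and section 7.1 states no hypotheses. The shift sizes, the numbers analysed below 50, the correlation r and the 95% interval itself are all assumptions made here.

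*(a) Coverage, in units of the score SD, n = 40.* SE of the mean change = sqrt(2(1 − r)/n).

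- r = 0.5: sqrt(1.0/40) = 0.158
- r = 0.7: sqrt(0.6/40) = 0.122

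Coverage of a nominal 95% interval under a shift b = Φ(1.96 − b/SE) − Φ(−1.96 − b/SE).

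| Assumed shift b | r = 0.5 | r = 0.7 |
|---|---|---|
| 0.1 SD | 90% | 87% |
| 0.2 SD | 76% | 63% |
| 0.3 SD | 53% | 31% |

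*(b) Apparent improvement when there is none, in units of the SD of change.* Half-width = t(0.975, n − 1)/sqrt(n), which is 0.284 at n = 50. The probability that the whole interval lies above zero comes from the noncentral t distribution with noncentrality b·sqrt(n). With no shift it would be 2.5%.

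| Assumed shift b | n = 50 | n = 40 | n = 35 |
|---|---|---|---|
| 0.1 | 10% | 9% | 8% |
| 0.2 | 28% | 23% | 21% |
| 0.3 | 55% | 46% | 41% |

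The SD of change is sqrt(2(1 − r)) score SDs, so the units of (a) and (b) coincide at r = 0.5. At r = 0.7 one SD of change is 0.775 score SD.

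The tables show how a pilot of this size would respond to a shift of a given size. They do not estimate the shift.

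**The case against.** A reader might infer that improvement is in fact inflated, that every self-reported score moves favourably, or that participants are assessed by their own coach. The protocol supports none of these. It speaks of CREs as a group and does not say that the individual coach performs the follow-up. It does not say whether the scales are read aloud or self-completed, and section 10.1 leaves open that REDCap is already meant for some of them. Direction is not certain either. Courtesy towards a coach does not supply correct answers on a knowledge test unless the coach prompts, and nothing suggests prompting. Training in symptom monitoring, or franker talk with a known educator, could worsen the CAT.

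The consequences are also limited. These are secondary endpoints of a pilot that plans no tests and states no confidence intervals. A uniform shift leaves the SD of change untouched, so only the use of the raw mean change as a target effect would carry the bias into the later trial, and section 7.2 does not say that this will be done. That change is hard to interpret in any case: section 7.3 restricts it to completers, and entry requires a recent exacerbation (section 4.4.1), which invites regression to the mean. Participants also know that they received the programme, so self-completion would remove only part of the bias.

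All of this stands as a limit on certainty and size. It does not remove the point: the protocol assigns coaching and outcome collection to the same staff group, and neither its safeguards nor its silence on mode protects the five scores.

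**Conclusion.** The concern holds as a risk built into the design. Followed as written, the plan leaves the CAT, mMRC, adapted COPD-Q, adapted COPD Self-Efficacy and Partners in Health change scores liable to a bias that acts after coaching and is probably favourable. There is no control group against which to judge it.

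Its size is unknown. The assumed shifts of 0.1, 0.2 and 0.3 SD give coverage of 87–90%, 63–76% and 31–53%, but these figures rest on n = 40, r = 0.5 to 0.7 and an interval that the protocol does not plan. They should not be read as a measure of the bias, nor as the gain from the fix, since some bias from unblinded self-report would persist. The primary feasibility endpoints are unaffected. The change is worth making because the means are already in the protocol and the cost is small.

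**What to change.** In sections 3.3, 6.1 and 7.4.3, state that the CAT, mMRC, adapted COPD-Q, adapted COPD Self-Efficacy Scale and Partners in Health Scale are self-completed by the participant through a REDCap link at baseline, 3 and 6 months, in the same mode each time, without a CRE administering them. The research assistant sends reminders, telephones non-responders only as back-up, and records the mode of completion. If section 10.1 already intends REDCap for some of these instruments, the amendment should name them there.

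The new mode must apply from baseline, since a switch between visits would itself affect the change scores.

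CREs continue to collect utilization, medication, smoking, vaccination and referral data, with confirmation from Epic. Study staff can see the questionnaire scores, so the safety review in sections 7.4.4 and 8.5 is unchanged.

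The cost is form set-up and a short amendment. REDCap is already used for case report forms (section 10.1) and e-consent (section 12.2), and a research assistant is already in place. The downside is possibly a few more missing or telephone-completed questionnaires. Telephone completion reintroduces some mixing of modes, which is why the mode should be recorded.

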6.2 Schedule of Events

Procedures	Screening Day -7 to -1	Baseline Visit 1, Day 1	Study Visit 2, 3 months	Study Visit 3, 6 months
Informed consent	X			
Confirming eligibility	X			
MLHC companion app orientation	X			
Demographic information	X			
Health system utilization		Χ	X	X
COPD severity (CAT and mMRC scores)		X	Х	X
Health-related quality of life (CAT score)		X	X	X
Mediation review		X	X	X
Smoking status review		Χ	X	X
Vaccination status review		Χ	X	X
Adapted COPD-Q score (knowledge of COPD)		Χ	X	X
Adapted COPD Self-Efficacy score		Χ	X	X
Partners in Health Scale score (self-management)		Χ	Χ	X
COPD referrals review (rehab, smoking cessation)		X	X	X
Adverse event review and evaluation		X	Х	X
Complete Case Report Forms (CRFs)	X	X	X	X

7.0 STATISTICAL CONSIDERATIONS

7.1 Statistical Hypotheses

This is a pilot study of feasibility, so there are no a priori null hypotheses to test

7.2 Sample Size Determination

As this is a pilot study, a sample size of 50 participants was chosen in order to adequately evaluate system feasibility first and foremost. The clinical outcomes of interest will be collected and analyzed, but the study will not be powered to capture a specific predicted difference at this stage. The results we do obtain will help inform the sample size calculations for a future larger clinical trial with control group.

7.3 Populations for Analyses

Feasibility outcomes will be assessed for all patients referred to study enrolment Clinical outcomes will be assessed for all patients who complete the MLHC program and provide follow-up information. Essentially a Per-Protocol Analysis format.

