2.0 CLINICAL TRIAL OBJECTIVES

2.1 Primary Objective

The primary objective is to evaluate the feasibility of delivering the MLHC program accompanied by the Epic Care Companion application. This will be evaluated by assessing system use over the study period, including the number of patients who start the program (over total number referred/offered), the number of patients who complete the program over the total number started, and the number of providers who refer patients to the program over the total number of eligible providers. We will also evaluate app use metrics by patients (number of interactions with the app, number of tasks completed, app features activated, time spent using the app)

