4.2 Participant Recruitment and Screening

We will target a recruitment of 50 patients with physician diagnosed COPD. The patients will be recruited from the WCH Respirology Program clinics (as patients must be followed at WCH in order to use the Epic Care Companion app component). Recruitment will be accomplished through: advertisement posters in the Respirology clinic directing patients to discuss participation with their WCH Respirologist, and referrals from clinicians/circle of care. The potential participant's respirolgist will be the one to determine interest/consent in the participant being contacted for the study.

Participants who have expressed interest in the study will be contacted by study personnel (for example, a research assistant) to discuss potential participation in the study. Patients will not be compensated for their participation.

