4.6 Screen Failures

We will collect screen failures demography, screen failure details, eligibility criteria, and any serious adverse events (SAE).

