7.4 Statistical Analyses

7.4.1 General Approach

7.4.2 Analysis of the Primary Endpoint(s)

Feasibility endpoints:

- MLHC program participation
 - Number of patients who started program over total offered
 - Number of patients who completed program over total started
 - o Number of providers who referred patients to the program over total
- MLCH Care Companion app use
 - o Number of times app opened
 - Number of sessions accessed within the app
 - Number of session tasks marked completed
 - Use of other app features (ex: medication reminder notifications)
 - Time spent using the app each time used

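### Does the first feasibility endpoint, program uptake, have conflicting denominators (offered, referred/offered, referred)?

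*Protocol*

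**What the plan says.** The uptake endpoint appears in the same words in the Clinical Trial Summary, in section 3.2 and in section 7.4.2: "Number of patients who started program over total offered". The primary objective in section 2.1 describes the measure as "the number of patients who start the program (over total number referred/offered", with both words inside one total. Section 7.3, on analysis populations, says: "Feasibility outcomes will be assessed for all patients referred to study enrolment".

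Section 4.2 sets out the route into the study. The patient's respirologist "will be the one to determine interest/consent in the participant being contacted for the study", and interested patients are then "contacted by study personnel (for example, a research assistant) to discuss potential participation in the study". Section 6.1 places informed consent, "Review of eligibility criteria" and orientation to the app in a single screening visit. Section 4.6 adds: "We will collect screen failures demography, screen failure details, eligibility criteria, and any serious adverse events (SAE". No section defines an offer or a referral.

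**The concern.** Uptake is the first feasibility endpoint listed, and section 7.2 justifies the 50 participants by the feasibility aim. With no hypothesis to test (section 7.1), the primary output is a set of descriptive figures, and a proportion means only what its denominator means.

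The two words can pick out different patients. If the offer is the respirologist's conversation, a patient who declines there has been offered the program but perhaps never referred. Uptake over referred patients is then higher than uptake over offered patients. If study staff make the offer after referral, a patient who is never reached has been referred but not offered, and uptake over referred patients is lower. The protocol does not say which applies.

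There is also a data question. If an offer includes the clinic conversation, refusals there have to be counted as they occur. Section 4.6 covers screen failures only, and the data sources named in section 10.1 are not said to record refusals before contact.

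**Working it through.** The protocol gives no expected uptake, precision or count for this endpoint, so there is no stated figure to reproduce. The check has two parts: comparing the sections, and asking how far the choice of denominator could move the result.

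**Comparing the sections**

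| Place | What it states | Group named |
|---|---|---|
| Summary, 3.2, 7.4.2 | the endpoint | offered |
| 2.1 | the objective | referred/offered, as one total |
| 7.3 | population for all feasibility outcomes | referred |

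1. The three statements of the endpoint agree.
2. Section 2.1 is the only place that uses both words for this ratio. It does not separate them and reads most naturally as one group under two names.
3. Section 7.3 covers every feasibility outcome at once. Completion is divided by starters, provider referral by providers, and the app measures describe users. Referred patients are the denominator of none of these, so 7.3 cannot be setting denominators. It tells the analyst not to restrict feasibility to program completers, in contrast to the per-protocol set that the same section gives for clinical outcomes.
4. Ineligible patients do not clearly separate the two groups. Consent and eligibility review fall in the same screening visit (6.1, 6.2), and signed consent is itself an inclusion criterion (4.4.1). A patient who fails there has normally been approached already. The group clearly referred but not offered is those never reached.
5. The third participation endpoint counts providers who referred patients, so referrals have to be captured. Starters over referred patients should therefore be available as a companion figure.

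**Size, by assumption**

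Let S be starters, O offered and R referred. Then (S/R) ÷ (S/O) = O/R.

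- Offer before referral, share q of offered patients declining: O = R/(1 − q), so O/R = 1/(1 − q) = 1.11, 1.25, 1.43 at q = 10, 20, 30%.
- Offer after referral, share f of referred patients never offered: O = R(1 − f), so O/R = 1 − f = 0.90, 0.80, 0.70 at f = 10, 20, 30%.

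Take S = 50, the target in section 4.2 ("We will target a recruitment of 50 patients with physician diagnosed COPD"), with all assumed to start, and assume R = 80. Then S/R = 50/80 = 62.5%.

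| Assumed loss | S/O if offer comes first: 62.5% × (1 − q) | S/O if offer comes second: 62.5% ÷ (1 − f) |
|---|---|---|
| 10% | 56.3% | 69.4% |
| 20% | 50.0% | 78.1% |
| 30% | 43.8% | 89.3% |

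Here f cannot exceed 30/80 = 37.5%, because offered patients cannot be fewer than the 50 starters.

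Whether such shifts exceed sampling error also depends on the assumptions. With 45 starters, a denominator of 60 gives 75.0% (Wilson 95% interval 62.8 to 84.2) and 75 gives 60.0% (48.7 to 70.3), and these intervals overlap. Denominators of 50 and 125 give 90.0% (78.6 to 95.7) and 36.0% (28.1 to 44.7), which do not. None of these denominators comes from the protocol.

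**The case for a change.** The strongest case for a change is that this goes beyond detail left to an SAP. The protocol itself names the group for a primary endpoint in five places and does not use one term. An analysis population ordinarily decides who enters a ratio, so a reader of 7.3 could reasonably divide by referred patients. An SAP written later could choose between the terms but could not recover refusals that nobody counted. Aligning the wording would cost very little.

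Part of this stands. The two words are undefined, 2.1 and 7.3 are loosely worded, and under one reading of an offer the refusals need counting from the start of recruitment.

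The rest is weaker. 7.3 cannot act as a denominator rule without making nonsense of the other feasibility outcomes, while 7.4.2 gives each participation ratio its own denominator. The worry about lost data needs the clinic-conversation reading of an offer, and it needs the Data Management Plan cited in section 10.1 to be silent. That plan is not at hand, and recruitment logging is the kind of detail such a document carries. Neither step can be established from the protocol.

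**Conclusion.** The concern does not call for a change. The endpoint is stated consistently as starters over offered patients, and an analyst following section 7.4.2 would report that. What is left is a gap in definition that an SAP or the Data Management Plan can fill in a sentence, and reporting the counts at each step would let a reader form either ratio.

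The size and direction of any discrepancy cannot be taken from the protocol; every percentage above rests on an assumed number referred and assumed losses. The protocol sets no uptake target or progression threshold and plans no test, so no stated decision turns on the figure.

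This conclusion assumes that 2.1 uses the two words for one group and that 7.3 describes whom the feasibility analysis covers. If the sponsor means an offer to include conversations in clinic, the count of refusals depends on recruitment records that the protocol does not describe. That is a matter of operational recording; the protocol states no rule here that would give a wrong result.
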